### **Randomized Phase 2 Dose Expansion:**

Approximately 120 female subjects who are post-menopausal with ER+/HER2- BrCa and who have had disease progression following endocrine therapy will be randomized in a 2:1 ratio to receive fulvestrant + GS-5829 or fulvestrant alone. Randomization will be stratified by prior cyclin-dependent kinase 4/6 (CDK4/6) inhibitor plus aromatase inhibitor (AI) status (naïve vs. progressed). The target number of subjects in each of the 2 strata will be approximately 60 (40 for GS-5829 in combination with fulvestrant and 20 for fulvestrant alone). GS-5829 and fulvestrant will be initiated on C1D1. Each cycle consists of 28 days.

Subjects may continue receiving GS-5829 once daily until disease progression (clinical or radiographic), unacceptable toxicity, withdrawal of consent, or death whichever comes first.

### **1.3. Sample Size and Power**

Up to approximately 40 subjects will be enrolled in the Phase 1b Dose Escalation portion of the study.

Total enrollment will be approximately 120 subjects in Randomized Phase 2 Dose Expansion portion. Approximately 80 subjects will be randomized to receive GS-5829 in combination with fulvestrant and 40 subjects will receive fulvestrant alone in a 2:1 ratio. One hundred twenty subjects will provide 88 events in total and greater than 90% power to detect the difference in PFS between the two treatment arms with 0.1 one-sided significance level, assuming a median PFS of 4 months for subjects who receive fulvestrant alone, a median PFS of 8 months in subjects who receive GS-5829 in combination with fulvestrant, accrual period of 9 months and total study duration of 19 months and a drop-out rate of 10% by 12 months. Within each stratum of naïve or progressed prior CDK4/6 inhibitor subjects, the power will be 80% with target number of 60 subjects (44 events).

## **2. TYPE OF PLANNED ANALYSIS**

### **2.1. Interim Analyses**

No formal interim analysis is planned for this study. Safety and tolerability will be monitored regularly for subjects in the study.

### **2.2. Final Analysis**

After all subjects have completed the study, outstanding data queries have been resolved or adjudicated as unresolvable, and the data have been cleaned and finalized, the final analysis of the data will be performed.

### **3. GENERAL CONSIDERATIONS FOR DATA ANALYSES**

Analysis results will be presented using descriptive statistics. For categorical variables, the number and percentage of subjects in each category will be presented; for continuous variables, the number of subjects (n), mean, standard deviation (StD), median, first quartile (Q1), third quartile (Q3), minimum, and maximum will be presented.

No formal statistical testing will be performed.

By-subject listings will be presented for all subjects in the All Enrolled Analysis Set and sorted by subject ID number, visit date, and time (if applicable). Data collected on log forms, such as AEs, will be presented in chronological order within the subject. The assigned treatment group and dose cohort will be used in the listings. Age, sex at birth, race, and ethnicity will be included in the listings, as space permits.

#### **3.1. Analysis Sets**

Analysis sets define the subjects to be included in an analysis. Analysis sets and their definitions are provided in this section. The analysis set will be identified and included as a subtitle of each table, figure, and listing.

For each analysis set, the number and percentage of subjects eligible for inclusion will be summarized by dose cohort within each treatment group.

A listing of reasons for exclusion from analysis sets will be provided by subject.

##### **3.1.1. All Enrolled Analysis Set**

All Enrolled Analysis Set includes all subjects who received a study subject identification number in the study after screening.

##### **3.1.2. Full Analysis Set**

The Full Analysis Set (FAS) includes all subjects who were enrolled and received at least 1 dose of any study drug (GS-5829, fulvestrant or exemestane). This is the primary analysis set for the analyses of efficacy. Throughout this SAP, study drug is defined as any drug in the combination therapy (GS-5829, fulvestrant or exemestane) unless specified otherwise.

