3.3. Study Treatments

Subjects who meet eligibility criteria will receive GS-5829 orally once daily combined with either 25 mg of exemestane orally once daily or with fulvestrant intramuscularly on Day 1, 15 (for whom C1D1 is the subject's first dose of fulvestrant), 29 and then every 28 days (\pm 3 days). Subjects in the Phase 1b Dose Escalation portion may initiate exemestane (Group A) or fulvestrant (Group B) any time prior to, or on, C1D1. Each cycle will consist of 28 days. Safety and efficacy assessments will occur on an outpatient basis including an assessment of tumor response, physical exam, vitals, ECG, collection of blood samples (for routine safety labs, GS-5829 pharmacokinetic, pharmacodynamic markers, and biomarkers at applicable visits), and assessment of AEs. In addition, subjects will undergo a CT scan (or MRI) scan every 8 weeks for the first year, then every 12 weeks.

Subjects who do not show evidence of disease progression may continue receiving GS-5829 combined with either exemestane (Group A) or fulvestrant (Group B) until disease progression (clinical or radiographic), unacceptable toxicity, withdrawal of consent, or death, whichever comes first.

Following treatment discontinuation, subjects will be followed for safety for 30 days from last dose of study drug. Subjects in the Randomized Phase 2 Dose Expansion portion of the study will also be followed for up to two years for OS from the last dose of study drug.

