## 1.2. Study Design

### Phase 1b Dose Escalation:

In the study, cohorts of postmenopausal women with advanced ER+/HER2- BrCa, for whom no standard curative therapy exists and who are candidates for exemestane or fulvestrant, will be sequentially enrolled at progressively higher dose levels of oral GS-5829 in combination with standard doses of exemestane or fulvestrant. The starting dose of GS-5829 has been determined to be 4 mg once daily based on safety information, pharmacokinetic and biomarker data from two ongoing GS-5829 studies (GS-US-350-1599, GS-US-350-1604) and the recommendation by the Bayesian Logistic Regression Model (BLRM) of dose-dose limiting toxicity (DLT) relationship.

Eligible subjects will be assigned to either Group A or B based on prior treatment. Group A will initiate with GS-5829 orally once daily on Cycle 1 Day 1 (C1D1) combined with 25 mg of exemestane administered orally once daily (or in accordance with locally approved labeling). The subject may initiate exemestane any time prior to, or on, C1D1. Enrollment in Group A will be stopped after completion of the 4 mg GS-5829 dose level safety assessments. Subjects who were previously enrolled/treated in Group A will continue to be followed and managed.

Group B will initiate GS-5829 orally once daily on C1D1, with fulvestrant administered intramuscularly (in accordance with locally approved labeling) every 28 days ( $\pm 3$  days). The subject may initiate fulvestrant any time prior to, or on, C1D1. For subjects whom are treatment

naïve (in metastatic setting) and for all subjects for whom C1D1 is the subject's first dose of fulvestrant, a one-time additional dose of 500 mg fulvestrant should be administered on Cycle 1 Day 15 (C1D15).

Subjects may continue receiving GS-5829 once daily until disease progression (clinical or radiographic), unacceptable toxicity, withdrawal of consent, or death, whichever comes first. Following treatment discontinuation, subjects will be followed for safety for 30 days from the last dose of study drug.

Study procedures at screening, baseline, and during the study treatment and follow-up are outlined in the protocol and presented in [Appendix 1: Study Procedures Table](#) of this SAP.

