### **3.8. Analysis Visit Windows**

#### **3.8.1. Definition of Study Day**

Study day will be calculated from the first dosing date of study drug and derived as follows:

- For postdose study days: Assessment Date – First Dosing Date + 1
- For days prior to the first dose: Assessment Date – First Dosing Date

Therefore, study day 1 is the day of the first dose of study drug administration.

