### **3.8.3. Selection of Data in the Event of Multiple Records in an Analysis Visit Window**

Depending on the statistical analysis method, single values may be required for each visit. For example, change from baseline by visit usually requires a single value, whereas a time-to-event analysis would not require 1 value per visit.

If multiple valid, nonmissing, continuous measurements exist in an visit, records will be chosen based on the following rules if a single value is needed:

- In general, the baseline value will be the last nonmissing value on or prior to Study Day 1, unless specified differently. If multiple measurements occur on the same day, the last nonmissing value prior to the first dosing date of study drug will be considered as the baseline value. If these multiple measurements occur at the same time or the time is not available, the average of these measurements (for continuous data) will be considered the baseline value.
- For postbaseline values:
  - The record closest to the nominal day for that visit will be selected.
  - If there are 2 records that are equidistant from the nominal day, the later record will be selected.
  - If there is more than 1 record on the selected day, the average will be taken, unless otherwise specified.

For central ECG data, there may be triplicates at the same nominal day/timepoint for each subject. The average of the triplicates should be used as baseline or postbaseline values at each visit and for selecting the maximum postbaseline values.

If multiple valid, nonmissing, categorical measurements exist in an analysis window, records will be chosen based on the following rules if a single value is needed:

- For baseline, the last available record on or prior to the date of the first dose of study drug will be selected. If there are multiple records with the same time or no time recorded on the same day, the value with the lowest severity will be selected (eg, normal will be selected over abnormal for safety electrocardiogram (ECG) findings).
- For postbaseline visits, if there are multiple records with the same time or no time recorded on the same day, the value with the worst severity within the window will be selected (eg, abnormal will be selected over normal for safety ECG findings).

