#### 4.2.1. Duration of Exposure to GS-5829

Total duration of exposure to GS-5829 will be defined as last dosing date of GS-5829 minus first dosing date of GS-5829 plus 1, regardless of any temporary interruptions in GS-5829 administration, and will be expressed in weeks using up to 1 decimal place (eg, 4.5 weeks).

If the last dosing date of GS-5829 is missing, the latest date among GS-5829 end date, clinical visit date, laboratory sample collection date, and vital signs assessment date that occurred during the on-treatment period will be used.

Partial dose start or stop dates for each dosing period will be imputed using the following algorithm:

- For dose stop date: If the day and month are missing but the year is available, then the imputed day and month will be the earliest from the following dates: 31 DEC, death date, end of treatment (EOT) date, EOS date, and (start date of the next dosing period – 1); If the day is missing but the month and year are available, , then the imputed day will be the earliest from the following dates: last day of the month, death date, EOT date, EOS date, and (start date of the next dosing period – 1).
- For dose start date: If the day and month are missing but the year is available, then the imputed day and month will be the earliest from the following dates: later of (01 JAN, and [stop date of the previous dosing period + 1]), and stop date of the associated dosing period; If the day is missing but the month and year are available, then the imputed day will be the earliest from the following dates: later of (first day of the month, and [stop date of the previous dosing period + 1]), and stop date of the associated dosing period.

The total duration of exposure to GS-5829 will be summarized using descriptive statistics and using number and percentage of subjects exposed through the following time periods: 1 day, 4 weeks, 8 weeks, 16 weeks, 24 weeks, 36 weeks and 48 weeks. Summaries will be provided by dose cohort within each treatment group for the Safety Analysis Set.

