## 6. EFFICACY ANALYSES

### 6.1. Definitions of Efficacy Endpoints

#### 6.1.1. Progression-free survival (PFS)

Progression-free survival (PFS), defined as the interval from first dosing date of study drug to the earlier of the first documentation of definitive disease progression or death from any cause. Definitive disease progression is determined based on RECIST Version 1.1 {[Eisenhauer 2009](#)}.

The date of definitive progression will be the time point at which progression is first identified by relevant radiographic, imaging, or clinical data. Data will be censored on the date of last adequate tumor assessment (i.e. not “Not Evaluable” [NE]) for subjects:

- who do not have documented progression or die, or
- who start new anticancer therapy before documented progression, or
- who start new anticancer therapy before death without documented progression, or
- who have  $\geq 2$  consecutive missing tumor assessments immediate before documented progression, or
- who have  $\geq 2$  consecutive missing tumor assessments immediate before death without documented progression

Subjects without any post-baseline tumor assessment will be censored at Study Day 1. If a subject does not have a baseline tumor assessment, then PFS will be censored at Study Day 1, regardless of whether or not definitive progression or death has been observed.

When the date of initiation of anticancer therapy other than the study treatment is incomplete or missing, the following algorithm will be followed:

- If the day is missing but the month and year are available, then the imputed day will be the last day of the month.
- If the day and month are missing but year is available, then the imputed day and month will be 01Jan or the last day of the month for the last non-NE tumor assessment if they have the same year, whichever is later.

Every attempt will be made to ensure that complete death dates are recorded. In those rare instances where complete death dates are not recorded, the following algorithm will be used:

- If the day is missing but the month and year are available, then the imputed day will be the midpoint of the month or the last assessment date + 1, whichever is later.

- If the day and month are missing but year is available, then the imputed day and month will be 01Jan or the last day of the latest month that the subject was known to be alive if they have the same year, whichever is later.

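### The SAP's definition of study drug leaves time zero open for Phase 1b subjects who start exemestane or fulvestrant before C1D1

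*SAP*

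**What the plan says.** The SAP's general definition stands in 3.1.2: "Throughout this SAP, study drug is defined as any drug in the combination therapy (GS-5829, fulvestrant or exemestane) unless specified otherwise". The time-zero rules use the term without qualifying it:

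- SAP 3.8.1: "Study day will be calculated from the first dosing date of study drug and derived as follows".
- SAP 3.8.3: "the baseline value will be the last nonmissing value on or prior to Study Day 1, unless specified differently". SAP 7.2.1 sets the laboratory baseline in the same way.
- SAP 6.1.1: PFS is "defined as the interval from first dosing date of study drug to the earlier of the first documentation of definitive disease progression". SAP 6.1.3 starts stable-disease duration at the same date.
- SAP 7.1.5.1 starts treatment-emergent adverse events at the study drug start date.

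The exposure rule in SAP 4.2.1, by contrast, names the drug: "last dosing date of GS-5829 minus first dosing date of GS-5829 plus 1".

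SAP 1.2 allows an early partner start in both groups. For Group A: "The subject may initiate exemestane any time prior to, or on, C1D1". For Group B, the subject "may initiate fulvestrant any time prior to, or on, C1D1". Protocol 3.3 agrees that Phase 1b subjects "may initiate exemestane (Group A) or fulvestrant (Group B) any time prior to, or on, C1D1". No limit on the lead time is stated. GS-5829 itself starts on C1D1.

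**The concern.** Take a subject already on exemestane or fulvestrant when GS-5829 is added. Under the SAP's own definition, her first dose of study drug is the partner dose. Her time zero then precedes C1D1, while visits (Protocol 6.5) and scans (Protocol Appendix 2) are counted from C1D1. The SAP never says how doses before C1D1 are to be classified, so two programmers could derive different study days from the same data.

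For such a subject, PFS and stable-disease duration would include time before the combination began, and the laboratory baseline would move earlier. Changes that arose before GS-5829 could be tabulated as treatment-emergent. The study stopped in Phase 1b (SAP 1), so these descriptive tables are its only efficacy and safety summaries. In cohorts of 3, one misdated subject shows.

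**Working it through.** The plan gives no figure of its own on this point, so the check is date arithmetic.

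**Inputs**

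- k = days from the first partner dose to C1D1. Not given; an assumption, shown over a range.
- Scans every 8 weeks ±7 days from C1D1 in year 1 (Protocol Appendix 2): Week 8 = day 56, Week 16 = day 112 (105 to 119), Week 24 = day 168 (161 to 175).
- Clinical benefit requires stable disease of at least 24 weeks = 168 days (SAP 6.1.3).
- Screening at most 28 days before C1D1 (Protocol synopsis, Screening). C1D1 pre-dose laboratory samples at most 2 days before the visit (Protocol 6.2.11).
- Cohorts of 3 (Protocol 3.2).

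**PFS and stable-disease duration**

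Literal study day of C1D1 = k + 1. Literal duration = duration from C1D1 + k (ignoring the +1 convention). Days from C1D1 needed for stable disease of 24 weeks = 168 − k.

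| k (days) | Study day of C1D1 | Week 8 progression | Week 16 progression | Days from C1D1 needed for 24 weeks |
|---|---|---|---|---|
| 0 | 1 | 56 | 112 | 168 |
| 7 | 8 | 63 | 119 | 161 |
| 28 | 29 | 84 | 140 | 140 |
| 56 | 57 | 112 | 168 | 112 |

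At k = 28 the increase is 84/56 = 1.50 (+50%) at Week 8 and 140/112 = 1.25 (+25%) at Week 16.

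For clinical benefit, a Week 24 scan done 1 to 7 days early needs only k of 1 to 7 days to reach 168 (168 − 161 = 7). Progression at Week 16 needs k = 168 − 112 = 56 days, or 168 − 119 = 49 to 168 − 105 = 63 over the scan window. One reclassified subject in a cohort of 3 moves the rate from 0/3 (Clopper-Pearson 95% CI 0 to 70.8%) to 1/3 (33.3%; 0.8 to 90.6%).

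**Laboratory baseline**

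The C1D1 pre-dose sample is drawn on day 0, −1 or −2 relative to C1D1. It falls on or before a partner start at day −k only if k is 2 or less, so from k = 3 it is always post-baseline. An earlier screening sample then becomes baseline, provided it was drawn on or before the partner start. At k above 28 no in-window screening sample can qualify, and SAP 7.2.2.1 counts any value of Grade 1 or higher as emergent. At shorter k this happens only if the partner dose preceded the screening sample. If the general baseline rule in SAP 3.8.3 were applied to scans, the same would hold for CT/MRI, and SAP 6.1.1 would censor PFS at Study Day 1.

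**Against the protocol**

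Protocol 8.6.3 starts laboratory emergence at C1D1. A SAP time zero before C1D1 would depart from that, although SAP 7.9 reports no departure from the protocol's safety analyses. The departure arises only if the earlier doses are recorded as study drug.

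**The case against.** The strongest reply is that the documents show what is meant. The protocol synopsis (Screening) and Protocol 5.1 place the first study drug dose on C1D1 or Day 1. Protocol 5.3 has study drug start after enrollment and cohort assignment, and has exemestane dispensed on the first day of each cycle. Protocol Appendix 2 gives fulvestrant at visits from C1D1. An earlier start of a commercial product fits naturally under prior anticancer therapy (SAP 5.4) or prior medication (SAP 7.4.1).

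Nor does the wording of SAP 4.2.1 prove that an unqualified study drug means any of the three. SAP 4.2.2.1 and 4.2.2.2 use the bare term for GS-5829 adherence and average dose. SAP 3.1.4 uses it for a 21-day rule that Protocol 6.12 states in GS-5829 doses.

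All of this stands. It makes C1D1 the likely intention and shows that the SAP's usage is loose. It does not remove the gap: the SAP's definition is stated to apply throughout, none of the time-zero rules overrides it, and no sentence classifies partner doses before C1D1.

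It is also fair that the largest effects need a partner start that normally predates screening. Protocol 6.4 screen-fails subjects not enrolled within 28 days, so a dose given after enrollment has k of about four weeks at most.

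**Conclusion.** The point holds as a minor, conditional one. It rests on two assumptions that the documents do not settle: that some Phase 1b subjects started the partner drug before C1D1, and that those doses are recorded as study drug. If either fails, there is no effect.

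Where both hold, PFS and stable-disease duration lengthen by k, normally by at most about 28 days, and from k = 3 the laboratory baseline moves earlier.

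Stronger readings that a reader might infer are not supported:

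- **That the SAP breaks the protocol's PFS clock.** Protocol 8.1.2 defines PFS from randomization, for Phase 2 only.
- **That SAP 7.9 is shown to be wrong.** The conflict with Protocol 8.6.3 is conditional.
- **That Week 16 progressions will count as clinical benefit, or that baselines will be lost.** The first needs k of 49 days or more. The second is certain only at k above 28, and otherwise needs a partner dose before the screening assessment. Both are unlikely.
- **That inference or dose selection is affected.** SAP 3 plans no formal testing, and Protocol 3.2 bases dose decisions on 28 days after C1D1 of GS-5829.

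**What to change.** In SAP 3.8.1, define the first dosing date and Study Day 1 as the date of the first GS-5829 dose (C1D1). Use it for study day, baseline, PFS, stable-disease duration and laboratory emergence. State that the tumor baseline is the assessment before C1D1, and that partner doses before C1D1 are prior therapy for these derivations. Give a fallback date for any subject in the Full Analysis Set without GS-5829, for example the enrollment date, which SAP 3.7 already uses for the age of undosed subjects. Keep the any-drug definition for analysis-set membership and for the window ending 30 days after the last dose.

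For adverse events, use the same C1D1 start and flag events between an early partner dose and C1D1 in the listings. The cost is that those events leave the treatment-emergent tables. If sites treated the partner dose as the start of study medication, Protocol 7.3 had all adverse events collected from then, so this could be more than a few; the number is not given.

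Otherwise the change is a few sentences and one derivation, with no new data. Separately, the protocol passages on when exemestane starts must be reconciled: the synopsis (test product) and 5.3 say on C1D1, while 3.3 and Appendix 2 allow an earlier start.

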##### **3.1.3. Safety Analysis Set**

The Safety Analysis Set includes all subjects who were enrolled and received at least 1 dose of any study drug. This is the primary analysis set for the analyses of safety, study drug administration and study drug compliance.

